6.1.2 DOSING AND ADMINISTRATION

Not Applicable

6.2 PREPARATION/HANDLING/STORAGE/ACCOUNTABILITY

6.2.1 ACQUISITION AND ACCOUNTABILITY

Not Applicable

6.2.2 FORMULATION, APPEARANCE, PACKAGING, AND LABELING

Not Applicable

6.2.3 PRODUCT STORAGE AND STABILITY

Not Applicable

6.2.4 PREPARATION

Not Applicable

6.3 MEASURES TO MINIMIZE BIAS: RANDOMIZATION AND BLINDING

Randomization:

Prior to randomization, patients will be stratified according to discharge location (home, inpatient rehabilitation). Within each stratum, patients will be randomly assigned in a 1:1 ratio to the X4 brace with the Motion Intelligence platform or standard of care.

The Biostatistics Unit will develop a randomization procedure using a permuted block design within the REDCap system). Additional details of the procedure, including required record keeping, will be further developed upon approval of this protocol. The Biostatistics Unit has extensive experience in implementing and in producing detailed documentation for such procedures.

Blinding and Concealed Allocation

Due to the nature of the X4 brace, it is not possible to blind the investigators or the participants. The randomization assignment will be obtained from BRMS, after consent has been obtained, after it has been determined that the subject has met all inclusion/exclusion criteria, and after the discharge location has been determined.

6.4 STUDY INTERVENTION COMPLIANCE

Patients randomized to the X4 brace cohort are required to access the system twice daily. Patients who have not accessed the system for over 72 hours will be contacted to determine the reason for non-compliance.

Compliance and adherence with the X4 brace with the Motion Intelligence platform are secondary outcomes of this study.

6.5 CONCOMITANT THERAPY

Not Applicable

6.5.1 RESCUE MEDICINE

Not Applicable

7 STUDY INTERVENTION DISCONTINUATION AND PARTICIPANT DISCONTINUATION/WITHDRAWAL

7.1 DISCONTINUATION OF STUDY INTERVENTION

Patients may discontinue using the X4 brace, however, this does not mean discontinuation from the study. The brace is single use and patients will not be required to return the brace.

7.2 PARTICIPANT DISCONTINUATION/WITHDRAWAL FROM THE STUDY

Participants are free to withdraw from participation in the study at any time upon request. All analyses will be carried out according the ITT principle. The ITT population will be all patients randomized, regardless of whether or not treatment was administered. All patients will be analyzed in the group to which they were randomized.

An investigator may discontinue or withdraw a participant from the study for the following reasons:

- Significant study intervention non-compliance
- A medical condition or situation occurs such that continued participation in the study would not be in the best interest of the participant

The reason for participant discontinuation or withdrawal from the study will be recorded in REDCap.

7.3 LOST TO FOLLOW-UP

A participant will be considered lost to follow-up if he or she fails to return for the 8 week postoperative visit and is unable to be contacted by the study site staff.

The site will attempt to contact the participant and reschedule the missed visit as soon as possible and counsel the participant on the importance of maintaining the assigned visit schedule and ascertain if the participant wishes to and/or should continue in the study. Before a participant is deemed lost to follow-up, the investigator or designee will make every effort to regain contact with the participant (where possible, 3 telephone calls and, if necessary, a certified letter to the participant's last known mailing address or local equivalent methods). These contact attempts should be documented in the participant's medical record or study file. Should the participant continue to be unreachable, he or she will be considered to have withdrawn from the study with a primary reason of lost to follow-up.

8 STUDY ASSESSMENTS AND PROCEDURES

8.1 EFFICACY ASSESSMENTS

Study Cohort Patients Only (Patients randomized to the X4 brace with the Motion Intelligence platform):

Patients will follow the prescribed exercises available on the patient application, with a number of the exercises actively tracked by the Mi360 sensor housed in the X4 brace. Compliance will be monitored by the physician and/or a delegated medical professional between postoperative visits on the Motion Intelligence dashboard.

Range of motion in flexion and extension will be measured twice daily within the patient application using the Mi360 sensor housed in the X4 brace. This information is then graphically presented on the home screen in the patient application over time. Range of motion can be tracked in real-time between postoperative visits by the physician and/or a delegated medical professional between postoperative visits on the Motion Intelligence dashboard.

Patient's will be required to access the application twice daily to enter their pain scores using the visual analog scale (0-10). Patient pain can be tracked in real-time by the physician and/or a delegated medical professional between postoperative visits on the Motion Intelligence dashboard.

All study patients:

All study patients will complete a daily "Daily Patient Log" starting the day after discharge from the hospital until postoperative day (POD) 56. This log will document the patient's location:

- Rehabilitation center or
- Home physical therapy or
- Physical therapy center
- Hospital (readmission)
- o Return to work (if applicable)

All study patients will be required to complete a preoperative and 8 week postoperative Knee Society Score questionnaire. This questionnaire is a standard of care for all total knee arthroplasty patients having surgery by Drs. [name] and [name].

8.2 SAFETY AND OTHER ASSESSMENTS

This clinical trial does not require any study specific screening tests or procedures. Preoperative screening done as part of the standard of care for a preoperative arthroplasty patient will be used to determine patient inclusion and exclusion. Additionally, there are no required on study lab testing or procedures required.

8.3 ADVERSE EVENTS AND SERIOUS ADVERSE EVENTS

8.3.1 DEFINITION OF ADVERSE EVENTS (AE)

Medical Device Reporting:

This clinical trial is evaluating a commercially available marketed medical device (X4 brace). The device is being used according to the manufacture's guidelines.

This study will adhere to the adverse event reporting regulations of the Centers for Devices and Radiological Health (CDRH), part of the Food and Drug Administration (FDA) regulations. In accordance with the Safe Medical Devices Act of 1990 (SMDA) (Public Law 102-629) (21 CFR 803.32 (c)) ambulatory surgery centers, hospitals, outpatient diagnostic centers and other user facilities are required to report all incidents in which a medical device or user error may have caused or contributed to the death, serious injury or serious illness of a patient.

Adverse Event Reporting Period

The study period during which adverse events must be reported is defined as the period from the initiation of any study procedures to the end of the study treatment follow-up. For this study, the initiation of study procedure will be from when the study subject starts using the X4 brace with the Motion Intelligence platform through the 8 week postoperative visit.

8.3.2 DEFINITION OF SERIOUS ADVERSE EVENTS (SAE)

Device User Facility Reporting Requirements of Serious Adverse Events:

A "device user facility" is a hospital, ambulatory surgical facility, nursing home, outpatient diagnostic facility, or outpatient treatment facility, which is not a physician's office. All deaths and serious injuries to which the device has or may have caused or contributed will be reported to the IRB, FDA and the manufacturer. The user facility will also submit annual reports to the FDA by January 1 of each year as described in 21 CFR 803.33.

Form 3419 Annual User Facility Report

- Medical Device Reporting Annual User Facility Report Form FDA3419
- Instructions for Completing the Medical Device Reporting Annual User Facility Report, Form FDA3419

Serious Injury or illness definition:

"Serious injury or illness" means those injuries that are life threatening, result in permanent body function impairment or permanent damage to a body structure, or necessitate immediate medical or

surgical intervention to prevent permanent body function impairment or permanent damage to a body structure (21 CFR 803.3) (r).

A device may have "caused or contributed to" a patient's death or serious injury, if the death or serious injury was or may have been attributed to the device or the device may have been a factor in the death or serious injury because of:

- Device failure
- \circ Malfunction
- Improper or inadequate device design
- Manufacture
- Labeling or
- o User error

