8.3.3 CLASSIFICATION OF AN ADVERSE EVENT

8.3.3.1 SEVERITY OF EVENT

All adverse events that do not meet any of the criteria for serious should be regarded as **non-serious adverse events**. Any non-serious adverse event felt to be related to the study device will be captured in the source documents and case report form.

- **Mild** Events require minimal or no treatment and do not interfere with the participant's daily activities.
- **Moderate** Events result in a low level of inconvenience or concern with the therapeutic measures. Moderate events may cause some interference with functioning.
- Severe Events interrupt a participant's usual daily activity and may require systemic drug therapy or other treatment. Severe events are usually potentially life-threatening or incapacitating. Of note, the term "severe" does not necessarily equate to "serious".

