8.3.6 SERIOUS ADVERSE EVENT REPORTING

The study investigator shall complete an Unanticipated Adverse Device Effect Form and submit to the reviewing Institutional Review Board (IRB) as soon as possible, but in no event later than 10 working

days after the investigator first learns of the effect. The investigator is responsible for conducting an evaluation of an unanticipated adverse device effect and shall report the results of such evaluation to the Food and Drug Administration (FDA). Thereafter, the investigator shall submit such additional reports concerning the effect as FDA requests.

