9.4.4 SAFETY ANALYSES

Safety Outcomes:

Outcomes for patients randomized to the X4 brace regardless of discharge location

- Adverse events: Each subject will be categorized at the end of the study as having had one or more adverse events, or not having had any adverse events.
- Serious adverse events: Each subject will be categorized at the end of the study as having had one or more adverse events, or not having had any serious adverse events.

Not Applicable

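### The trial's only definition of a serious adverse event is the FDA device-injury rule, so a device-related readmission can count as non-serious in 9.4.4 and an unrelated death has no clear status

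*Combined protocol and SAP*

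**What the plan says.** Section 8.3.2, headed as the definition of serious adverse events, sets out device user facility reporting. Its definition of serious injury or illness "means those injuries that are life threatening, result in permanent body function impairment or permanent damage to a body structure". It also covers injuries for which immediate intervention is needed to avert such harm, and it cites 21 CFR 803.3. On death it sets a reporting duty, which extends to the manufacturer as well: "All deaths and serious injuries to which the device has or may have caused or contributed will be reported to the IRB, FDA and the".

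Section 8.3.3.1 sorts the remainder as non-serious, in a sentence that opens: "All adverse events that do not meet any of the criteria for serious should be regarded as". Section 8.3.6, on reporting serious events, names one form: "The study investigator shall complete an Unanticipated Adverse Device Effect Form".

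Section 9.4.4 uses the term for an outcome in the X4 arm: "Serious adverse events: Each subject will be categorized at the end of the study". The first of its two categories is patients with at least one adverse event, without the word *serious*. The second is patients with no serious adverse event.

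Sections 4.1 and 8.1 have all patients in both arms keep a Daily Patient Log from the day after hospital discharge to postoperative day 56. Hospital readmission is one of its entries.

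**The concern.** A threshold written for mandatory reports to FDA and the manufacturer is doing the work of a trial outcome definition. The two have different purposes. The regulatory rule selects device-caused harm that is grave or permanent. A trial's SAE count is normally read as covering hospitalisation and death as well, and a reader of the published result would assume that it does.

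Monitoring device-related adverse events is a primary safety objective (synopsis and section 3), and 9.4.4 classifies each X4 patient on serious events. If a brace-related problem put a patient back in hospital without threatening life or permanent function, the trial could log the readmission, record the event as an adverse event, and still report that no serious adverse event occurred.

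**Working it through.** The plan gives no figure on readmissions or serious events, so there is nothing to recompute. The check is to apply the rules to the cases that matter and then compare the capture rules.

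**1. Classification.** Inputs: the definition in 8.3.2, the residual rule in 8.3.3.1 and the variable in 9.4.4, read as it was presumably intended (patients with a serious event).

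| Event in an X4 patient | Meets 8.3.2? | Result in 9.4.4 |
|---|---|---|
| Device-related readmission, life threatening | Yes | Serious |
| Device-related readmission, immediate intervention needed to prevent permanent harm | Yes | Serious |
| Device-related readmission, neither of these and no permanent damage | No | Non-serious; counted only in the any-AE line |
| Death to which the device may have contributed | Reportable under 8.3.2, though not in the definition sentence | Presumably serious |
| Death unrelated to the device | Not addressed | Unclear |

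The third and fifth rows are the gap. No section makes hospitalisation or readmission a seriousness criterion, and no section links the Daily Patient Log to adverse event classification.

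**2. The SAE line in 9.4.4 taken literally.** Category A is at least one adverse event of any kind. Category B is no serious adverse event. A patient with one mild adverse event belongs to both. The categories overlap, so the variable cannot be derived as written.

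**3. Which events are recorded.**

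- 8.3.3.1: non-serious events felt to be device-related go to source documents and the CRF.
- 8.3.4: all adverse events, including those that miss the SAE criteria, go on the CRF, and all on-study events are documented whatever their relationship to the device.
- 8.3.5: events expected after arthroplasty are not adverse events for the eCRF, and no study-related events are taken to occur in controls.
- 8.3.6: the only per-event form named is for unanticipated device effects.
- 10.1.9.1: clinical data, including device-related adverse events, are entered in REDCap.

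These do not give one answer. Dehydration is on the expected list in 8.3.5. A readmission for dehydration would be documented under 8.3.4 but is kept out of the eCRF by 8.3.5.

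**The case against.** The strongest reply is that little is lost. The primary safety endpoint is device-related adverse events, not SAEs. A device-related readmission that misses 8.3.2 is still recorded, graded for severity up to severe, assessed for relationship, and counted in the any-AE line of 9.4.4. That stands: the fault is one of labelling and of an undefined variable, not of vanished data.

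Some stronger readings are tempting, and the documents do not support them.

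- *Anticipated serious events have no route into the data.* Section 8.3.4 does not confine the CRF to non-serious events; it covers all adverse events, non-serious ones included. Section 10.1.9.1 sends device-related events to REDCap with no limit on seriousness.
- *Death is left out.* Section 8.3.2 makes deaths reportable when the device may have contributed. Only the unrelated death is unaddressed.
- *The unanticipated-effect form is the only form for serious events.* Section 8.3.2 also names another: "Medical Device Reporting Annual User Facility Report Form FDA3419". That is an annual facility report, so the accurate statement is that 8.3.6 names no other per-event form.
- *The SAE count will be near zero unless harm is permanent.* Life-threatening events qualify without permanent harm, as do those needing immediate intervention to prevent it.
- *A number of missed events can be given.* An assumed readmission rate of 2% to 6% in the 120 planned X4 patients gives 120 × 0.02 = 2.4 to 120 × 0.06 = 7.2 readmissions. That is an all-cause figure on an assumed rate. Nothing in the documents says what share would be device-related or would miss the 8.3.2 criteria.

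**Conclusion.** The point holds in a limited form. The device-injury rule is the only definition of serious in the plan. Under it, a device-related readmission that is not life threatening, causes no permanent damage and needs no immediate intervention to prevent such damage is non-serious by rule. The status of an unrelated death in 9.4.4 is unclear. Separately, the SAE line in 9.4.4 has overlapping categories, and five sections need reconciling on which events are recorded.

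No magnitude is claimed. The conclusion rests on the wording alone and on one assumption: that 9.4.4, having no definition of its own, takes its meaning of serious from 8.3.2. It affects how the safety result is labelled and read. It does not touch the efficacy analysis.

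**What to change.** - Keep the 21 CFR 803 definition in 8.3.2 for reports to FDA and the manufacturer, and say that this is its purpose.
- For the trial's SAE variable (8.3.2, 8.3.3.1, 9.4.4), add death from any cause and hospital readmission through the 8-week visit. Record each on the CRF with its relationship to the brace, whether or not it was anticipated.
- Use the Daily Patient Log to find readmissions. The log stops at day 56 and has no entry for death, so deaths, and readmissions between day 56 and a later 8-week visit, must come from site follow-up.
- Correct the first SAE category in 9.4.4 so that it refers to serious adverse events.
- Reconcile 8.3.3.1, 8.3.4, 8.3.5, 8.3.6 and 10.1.9.1 on which events are captured and on which form.
- Report device-related SAEs in the X4 arm. Report all-cause readmission and death in both arms, taking readmission from the log. An X4-only all-cause count could not be separated from the background of surgery.

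The cost is protocol and SAP wording, a small CRF addition, a few more SAE records and a less favourable SAE count. The log data are already planned for every patient.

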8.3.3 CLASSIFICATION OF AN ADVERSE EVENT

8.3.3.1 SEVERITY OF EVENT

All adverse events that do not meet any of the criteria for serious should be regarded as **non-serious adverse events**. Any non-serious adverse event felt to be related to the study device will be captured in the source documents and case report form.

- **Mild** Events require minimal or no treatment and do not interfere with the participant's daily activities.
- **Moderate** Events result in a low level of inconvenience or concern with the therapeutic measures. Moderate events may cause some interference with functioning.
- Severe Events interrupt a participant's usual daily activity and may require systemic drug therapy or other treatment. Severe events are usually potentially life-threatening or incapacitating. Of note, the term "severe" does not necessarily equate to "serious".

8.3.3.2 RELATIONSHIP TO STUDY INTERVENTION

All adverse events (AEs) must have their relationship to study intervention (device) assessed by the clinician who examines and evaluates the participant based on temporal relationship and his/her clinical judgment. The degree of certainty about causality will be graded using the categories below. In a clinical trial, the study product must always be suspect.

- **Related** The AE is known to occur with the study intervention, there is a reasonable possibility that the study intervention caused the AE, or there is a temporal relationship between the study intervention and event. Reasonable possibility means that there is evidence to suggest a causal relationship between the study intervention and the AE.
- Not Related There is not a reasonable possibility that the administration of the study intervention caused the event, there is no temporal relationship between the study intervention and event onset, or an alternate etiology has been established.

8.3.3.3 EXPECTEDNESS

The Principal Investigator will be responsible for determining whether an adverse event (AE) is expected or unexpected. An AE will be considered unexpected if the nature, severity, or frequency of the event is not consistent with the risk information previously described for the study intervention.

8.3.4 TIME PERIOD AND FREQUENCY FOR EVENT ASSESSMENT AND FOLLOW-UP

The occurrence of an adverse event (AE) or serious adverse event (SAE) may come to the attention of study personnel during study visits and interviews of a study participant presenting for medical care.

All AEs including local and systemic reactions not meeting the criteria for SAEs will be captured on the appropriate case report form (CRF). Information to be collected includes event description, time of onset, clinician's assessment of severity, relationship to study product (assessed only by those with the training and authority to make a diagnosis), and time of resolution/stabilization of the event. All AEs occurring while on study must be documented appropriately regardless of relationship. All AEs will be followed to adequate resolution.

Changes in the severity of an AE will be documented to allow an assessment of the duration of the event at each level of severity to be performed. AEs characterized as intermittent require documentation of onset and duration of each episode.

At each study visit, the investigator will inquire about the occurrence of AE/SAEs since the last visit. Events will be followed for outcome information until resolution or stabilization.

8.3.5 ADVERSE EVENT REPORTING

This clinical trial consists of postoperative total knee arthroplasty patients. DRE's common and expected in this group of patients include postoperative pain, nausea, hypotension, anemia, and dehydration. Events anticipated and expected in the postoperative arthroplasty patient will not be considered an adverse event for collection in the eCRF. Additionally, there are no study interventions for the control group. This group will be following the standard of care treatment for a total knee arthroplasty patient. Therefore, no adverse events related to the study will be occurring in this group.

8.3.6 SERIOUS ADVERSE EVENT REPORTING

The study investigator shall complete an Unanticipated Adverse Device Effect Form and submit to the reviewing Institutional Review Board (IRB) as soon as possible, but in no event later than 10 working

days after the investigator first learns of the effect. The investigator is responsible for conducting an evaluation of an unanticipated adverse device effect and shall report the results of such evaluation to the Food and Drug Administration (FDA). Thereafter, the investigator shall submit such additional reports concerning the effect as FDA requests.

8.3.7 REPORTING EVENTS TO PARTICIPANTS

Not Applicable

